### 3 Dual-Frequency Transducers:

The probes we plan to use in this study are modified VisualSonics RMV716 probes. They have been modified to house a high frequency inner element and a low frequency annular ring element, instead of a single transducer element. We plan to run the transducers in dual-frequency contrast mode during the study. In dual-frequency contrast mode, the low frequency (outer) element transmits ultrasound and the

high frequency (outer) element ring receives the signal. In this mode, the low frequency element is run by an external waveform generator and amplifier, and the high frequency element is run by the Vevo 770 system.

**Figure 2.** Device Transducers

## 5.1 Expected Risks

### 5.1.1 VisualSonics Vevo 770

This research protocol presents minimal risk to participants, investigators and study personnel. The ultrasound imaging equipment, though specifically designed for preclinical use and not FDA approved, is calibrated and will be used according to FDA limits on diagnostic imaging ultrasound exposure to patients (Mechanical Index of less than 1.9 and spatial-peak temporal average intensity of less than 720 mW/cm^2). For

the imaging studies proposed here, the maximum mechanical index and intensity will not exceed 0.8 and 300 mW/cm^2, respectively, less than half of the FDA limits, and within the range of standard output parameters regularly used in diagnostic ultrasound imaging. Furthermore, this is within the mechanical index range listed on the prescribing information for use of perflutren contrast agent. The 1.5 cycle pulse length and 2-4 MHz center frequency of the ultrasound that is produced by our transducers are within the range of common parameters regularly used by other FDA approved diagnostic ultrasound imaging systems. The unique aspect of this imaging system is that we receive data at a higher frequency (15-45 MHz) than typical diagnostic ultrasound imaging systems used for transcutaneous imaging. The transmitted ultrasound parameters are within standard diagnostic imaging ranges for frequency and acoustic output.

### 5.1.2 Perflutren lipid (Definity)

See sections 1.4 and 6.1.5.

## 5.2 Duration of Study

It is anticipated that the total study duration encompassing recruitment, enrollment, and data analysis will take approximately 2 years. Active patient participation will last approximately 1 visit (consent and 15 minutes imaging).

## 6.0 Drug Information

### 6.1 Perflutren Lipid Microspheres (Lantheus Medical Imaging)

The Definity® vial contains components that upon activation yield perflutren lipid microspheres composed of octafluoropropane. Perflutren is a diagnostic drug that is intended to be used for contrast enhancement. The vial contains a clear, colorless, sterile, non-pyrogenic, hypertonic solution which is activated by mechanical agitation with Vialmix®. Vialmix® is the activation device for use in the preparation of US contrast imaging agents, including Definity®. Prior to activation, each Definity® vial contains 6.52 mg/mL octafluoropropane in the headspace and 0.75 mg lipid blend (0.045 mg DPPA, 0.401 mg DPPC, and 0.304 mg MPEG5000 DPPE), 103.5 mg propylene glycol, 126.2 mg glycerin, 2.34 mg sodium phosphate monobasic monohydrate, 2.16 mg sodium phosphate dibasic heptahydrate and 4.87 mg sodium chloride in water in the clear liquid. Upon activation, each mL of the milky white suspension contains a maximum of 1.2 x 10^10 perflutren lipid microspheres with approximately 150 µL/mL octafluoropropane.

### 6.1.1 Supplier/How Supplied

Perflutren (Definity®) will be provided to study subjects at no cost. Perflutren is supplied as a single use 2mL clear glass vial containing clear liquid. Each package contains 4 single-use vials.

### 6.1.2 Handling and Dispensing of Perflutren

Perflutren lipid must be dispensed only from official study sites by authorized personnel according to local regulations. Perflutren should be stored in a secure area according to local regulations. It is the responsibility of the Investigator to ensure that study drug is only dispensed to study patients.

### 6.1.3 Storage Requirements/Stability

The drug product should be stored in a secure location with limited access under controlled temperature conditions of 2-8° C (36° -46° F) in a refrigerator.

### 6.1.4 Preparation

See [http://www.definityimaging.com/pdf/VIALMIX\\_Users\\_Guide.pdf](http://www.definityimaging.com/pdf/VIALMIX_Users_Guide.pdf), and the package insert for instructions on the use of Vialmix®.

### 6.1.5 Clinical Safety Summary

See prescribing information on perflutren when used according to its FDA indication (<http://www.accessdata.fda.gov/scripts/cder/drugsatfda/>), and see section 1.3 for a summary of toxicities reported in clinical trials. In addition, the following warnings and precautions are noted in the October 2011 labeling:

#### *Serious Cardiopulmonary Reactions:*

Serious cardiopulmonary reactions including fatalities have occurred uncommonly during or shortly following perflutren-containing microsphere administration, typically within 30 minutes of administration. The risk for these reactions may be increased among patients with unstable cardiopulmonary conditions (acute myocardial infarction, acute coronary artery syndromes, worsening or unstable congestive heart failure, or serious ventricular arrhythmias). Always have cardiopulmonary resuscitation personnel and equipment readily available prior to perflutren administration and monitor all patients for acute reactions.

The reported reactions include: fatal cardiac or respiratory arrest, shock, syncope, symptomatic arrhythmias (atrial fibrillation, tachycardia, bradycardia, supraventricular tachycardia, ventricular fibrillation, ventricular tachycardia), hypertension, hypotension, dyspnea, hypoxia, chest pain, respiratory distress, stridor, wheezing, loss of consciousness, and convulsions.

#### *Anaphylactoid Reactions:*

In post-marketing use, uncommon but serious anaphylactoid reactions were observed during or shortly following perflutren-containing microsphere administration including: shock, hypersensitivity, bronchospasm, throat tightness, angioedema, edema (pharyngeal, palatal, mouth, peripheral, localized), swelling (face, eye, lip, tongue, upper airway), facial hypoesthesia, rash, urticaria, pruritus, flushing, and erythema have occurred in patients with no prior exposure to perflutren-containing microsphere products.

*Systemic Embolization of Perflutren in Patients with Cardiac Shunts:*

In patients with right-to-left, bi-directional, or transient right-to-left cardiac shunts phospholipid-encapsulated microspheres can bypass the pulmonary particle-filtering mechanisms and directly enter the arterial circulation resulting in microvascular occlusion and ischemia. In an animal study utilizing intra-arterial administration of activated perflutren, microsphere trapping was seen in small arterioles <15 µm, especially at branch points and in capillaries at all doses tested, including doses directly applicable to those used in humans. An animal study utilizing intravenous 15 administration did not result in arterial microvascular obstruction presumably because of filtering by the lungs. Do not administer perflutren by intra-arterial injection.

*High Ultrasound Mechanical Index:*

High ultrasound mechanical index values may cause microsphere cavitation or rupture and lead to ventricular arrhythmias. Additionally, end-systolic triggering with high mechanical indices has been reported to cause ventricular arrhythmias. The safety of activated perflutren at mechanical indices greater than 0.8 has not been evaluated.

*QTc Prolongation:*

ECG parameters for doses up to 10 microL/kg were monitored in 221 subjects at multiple time points from 1 hour to 72 hours after the first bolus injection. In the 221 subjects, QTc prolongations of >30 msec were noted in 64 (29%) subjects. Forty-six out of 64 subjects with QTc prolongations were further evaluated and 39% (18/46) showed associated cardiac rhythm changes. The effects of concomitant drugs were not studied.

**6.1.6 Return and Retention of Study Drug**

Incomplete vials of perflutren lipid remaining at the completion of the study, or expired perflutren lipid will be destroyed by UNC IDS.

**7.0 ADVERSE EXPERIENCES-DRUGS**

## 7.1 Definitions

### 7.1.1 Adverse Event (AE)

An adverse event (AE) is any untoward medical occurrence (e.g., an abnormal laboratory finding, symptom, or disease temporally associated with the use of a drug) in a patient or clinical investigation subject administered a pharmaceutical product and which does not necessarily have a causal relationship with this treatment. An AE can therefore be any unfavorable and unintended sign (including an abnormal laboratory finding), symptom, or disease temporally associated with the use of a medicinal product, whether or not related to the medicinal product.

Hospitalization for elective surgery or routine clinical procedures that are not the result of an AE (e.g., surgical insertion of central line) need not be considered AEs and should not be recorded as an AE. Disease progression should not be recorded as an AE, unless it is attributable by the investigator to the study therapy.

### 7.1.2 Suspected Adverse Reaction (SAR)

A suspected adverse reaction (SAR) is any AE for which there is a *reasonable possibility* that the drug is the cause. *Reasonable possibility* means that there is evidence to suggest a causal relationship between the drug and the AE. A suspected adverse reaction implies a lesser degree of certainty about causality than adverse reaction, which means any adverse event caused by a drug.

Causality assessment to a study drug is a medical judgment made in consideration of the following factors: temporal relationship of the AE to study drug exposure, known mechanism of action or side effect profile of study treatment, other recent or concomitant drug exposures, normal clinical course of the disease under investigation, and any other underlying or concurrent medical conditions. Other factors to consider in considering drug as the cause of the AE:

- Single occurrence of an uncommon event known to be strongly associated with drug exposure (e.g., angioedema, hepatic injury, Stevens-Johnson Syndrome)
- One or more occurrences of an event not commonly associated with drug exposure, but otherwise uncommon in the population (e.g., tendon rupture); often more than once occurrence from one or multiple studies would be needed before the sponsor could determine that there is *reasonable possibility* that the drug caused the event.
- An aggregate analysis of specific events observed in a clinical trial that indicates the events occur more frequently in the drug treatment group than in a concurrent or historical control group

### 7.1.3 Unexpected AE or SAR

An AE or SAR is considered unexpected if the sensitivity and specificity or severity of it is not consistent with the applicable product information (e.g., Investigator's Brochure (IB) for an unapproved investigational product or package insert/summary of product characteristics for an approved product). Unexpected also refers to AEs or SARs that are mentioned in the IB as occurring with a class of drugs or as anticipated from the pharmacological properties of the drug, but are not specifically mentioned as occurring with the particular drug under investigation.

### 7.1.4 Serious AE or SAR

An AE or SAR is considered serious if, in the view of either the investigator or sponsor, it results in any of the following outcomes:

- Death;
- Is life-threatening (places the subject at immediate risk of death from the event as it occurred);
- Requires inpatient hospitalization (>24 hours) or prolongation of existing hospitalization;\*
- Results in congenital anomaly/birth defect;
- Results in a persistent or significant incapacity or substantial disruption of the ability to conduct normal life functions;
- Important medical events that may not result in death, be life-threatening, or require hospitalization may be considered a serious adverse drug experience when, based upon appropriate medical judgment, they may jeopardize the patient or subject and may require medical or surgical intervention to prevent one of the outcomes listed in the definition. For reporting purposes, also consider the occurrences of pregnancy as an event which must be reported as an important medical event.

\*Hospitalization for anticipated or protocol specified procedures such as administration of chemotherapy, central line insertion, metastasis interventional therapy, resection of primary tumor, or elective surgery, will not be considered serious adverse events.

Pregnancy that occurs during the study must also be reported as an SAE.

## 7.2 Documentation of non-serious AEs or SARs

For non-serious AEs or SARs, documentation must begin from day 1 of study treatment and continue through the 30 day follow-up period after treatment is discontinued.

Collected information should be recorded in the electronic Case Report Forms (e-CRF) for that patient. Please include a description of the event,

its severity or toxicity grade, onset and resolved dates (if applicable), and the relationship to the study drug. Documentation should occur at least monthly.

### **7.3 SAEs or Serious SARs**

#### **7.3.1 Timing**

After informed consent but prior to initiation of study medications, only SAEs caused by a protocol-mandated intervention will be collected (e.g. SAEs related to invasive procedures such as biopsies, medication washout, or no treatment run-in).

For any other experience or condition that meets the definition of an SAE or a serious SAR, recording of the event must begin from day 1 of study treatment and continue through the 30 day follow-up period after treatment is discontinued.

#### **7.3.2 Documentation and Notification**

These events (SAEs or Serious SARs) must be recorded for that patient within 24 hours of learning of its occurrence.

#### **7.3.3 Reporting**

##### **IRB Reporting Requirements:**

- UNC will submit an aggregated list of all SAEs to the UNC IRB annually at the time of study renewal according to the UNC IRB policies and procedures.
- The UNC-IRB will be notified of all SAEs that qualify as an Unanticipated Problem as per the UNC IRB Policies using the IRB's web-based reporting system (see section 8.2 ) within 7 days of the Investigator becoming aware of the problem.

##### Pregnancy

Pregnancies and suspected pregnancies (including a positive pregnancy test regardless of age or disease state) of a female subject occurring while the subject is on study should be recorded as SAEs. The patient is to be discontinued immediately from the study. The female subject should be referred to an obstetrician-gynecologist, preferably one experienced in reproductive toxicity for further evaluation and counseling.

The Investigator will follow the female subject until completion of the pregnancy, and must document the outcome of the pregnancy (either normal or abnormal outcome). If the outcome of the pregnancy was abnormal (e.g., spontaneous or therapeutic abortion), the Investigator should report the abnormal outcome as an AE. If the abnormal outcome meets any of the serious criteria, it must be reported as an SAE.

## 8.0 UNANTICIPATED CONCERNS

### 8.1 Unanticipated Adverse Device Effect (UADE)

The investigational device exemption (IDE) regulations define an unanticipated adverse device effect (UADE) as “any serious adverse effect on health or safety or any life-threatening problem or death caused by, or associated with, a device, if that effect, problem, or death was not previously identified in nature, severity, or degree of incidence in the investigational plan or application (including a supplementary plan or application), or any other unanticipated serious problem associated with a device that relates to the rights, safety, or welfare of subjects” (21 CFR 812.3(s)).

### 8.2 Unanticipated Problems (UP)

As defined by UNC’s IRB, unanticipated problems involving risks to study subjects refers to any incident, experience, or outcome that:

- Is unexpected (in terms of nature, severity, or frequency) given (a) the research procedures that are described in the protocol-related documents, such as the IRB-approved research protocol and informed consent document; and (b) the characteristics of the subject population being studied;
- Is related or possibly related to a subject’s participation in the research; and
- Suggests that the research places subjects or others at a greater risk of harm (including physical, psychological, economic, or social harm) related to the research than was previously known or recognized.

### 8.3 Reporting

#### 8.3.1 UADEs

UADEs must be reported by the clinical investigator to the sponsor and the reviewing IRB, as described below:

For this device study, investigators are required to submit a report of a UADE to the FDA, the manufacturer of the device and the UNC IRB as soon as possible, but in no event later than 10 working days after the investigator first learns of the event (§ 812.150(a)(1)), using the MedWatch Form 3500A. Sponsors (LCCC) must immediately conduct an evaluation of a UADE and must report the results of the evaluation to FDA, the UNC IRB, and participating investigators within 10 working days after the sponsor first receives notice of the effect (§§ 812.46(b), 812.150(b)(1)).

For this device study, we will submit a report of a UADE to the manufacturer and the IRB as soon as possible, but no later than 10 working days after the investigators first learn of the event.

### 8.3.2 UP

Any events that meet the criteria for “Unanticipated Problems” as defined by UNC’s IRB must be reported by the Study Coordinator using the IRB’s web-based reporting system.

Any unanticipated problem that occurs during the conduct of this study and that meets **at least** the first two criteria listed in section 8.2 must be reported to the UNC IRB using the IRB’s web-based reporting system.

## 9.0 Data and Safety Monitoring Plan

The Principal Investigator will provide continuous monitoring of patient safety in this trial with periodic reporting to the Data and Safety Monitoring Committee (DSMC).

Meetings/teleconferences will be held at a frequency dependent on study accrual, and in consultation with the study Biostatistician. These meetings will include the investigators as well as protocol nurses, clinical research associates, regulatory associates, data managers, biostatisticians, and any other relevant personnel the principal investigators may deem appropriate. At these meetings, the research team will discuss all issues relevant to study progress, including enrollment, safety, regulatory, data collection, etc.

The team will produce summaries or minutes of these meetings. These summaries will be available for inspection when requested by any of the regulatory bodies charged with the safety of human subjects and the integrity of data including, but not limited to, the oversight (Office of Human Research Ethics (OHRE) Biomedical IRB, the Oncology Protocol Review Committee (PRC) or the North Carolina TraCS Institute Data and Safety Monitoring Board (DSMB).

The UNC LCCC Data and Safety Monitoring Committee (DSMC) will review the study on a regular (quarterly to annually) basis, with the frequency of review based on risk and complexity as determined by the UNC Protocol Review Committee. The UNC PI will be responsible for submitting the following information for review: 1) safety and accrual data including the number of patients treated; 2) significant developments reported in the literature that may affect the safety of participants or the ethics of the study; 3) preliminary response data; and 4) summaries of team meetings that have occurred since the last report. Findings of the DSMC review will be disseminated by memo to the UNC PI, PRC, and the UNC IRB and DSMB.

## 10.0 STATISTICAL CONSIDERATIONS

This is a nonrandomized, single-center study. The primary purpose and endpoint of this study is to compare, in a radiologist reader study, the sensitivity and specificity of the acoustic angiography system to the b-mode ultrasound with pathology as the reference standard.

### 10.1 Sample Size and Accrual

Per the revision in increased Perflutren dose, we have updated our sample size statistics as follows.

For power calculation, the null hypothesis is that the specificity of acoustic angiography system is the same as the standard of care (b-mode ultrasound), which is assumed to be 70%. (We will determine the specificity of b-mode ultrasound during the trial to confirm that the 70% represents the specificity in the hands of UNC radiologists) Under the alternative, we expect that the specificity of the new device is at least 90%. The specificities are measured relative to pathological diagnosis as the reference standard. With 60 lesions and 5 readers, where we anticipate that roughly half will be malignant, assuming the correlation from the same patient to be 0.5 and the readers to read different patients independently, the power to see specificity at least larger than 90% is 98% at the significance level 0.05 using one-side test. With 50 lesions (half are benign), the power to see specificity of 90% is >96%; with 25 lesions (about 13 are benign), this power becomes 72%. The power to reject the null hypothesis is 98%. Although we will study both sensitivity and specificity, our power calculation is based on specificity, which is the primary interest.

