## 2.0 STUDY OBJECTIVES AND ENDPOINTS

### 2.1 Primary Objective

To compare (using a reader study) the sensitivity and specificity of acoustic angiography to the sensitivity and specificity of conventional b-mode ultrasound in evaluation of breast lesions

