#### 4.2 Enrollment/Recruitment

A total of 60 women will be enrolled to this study. The 60 study subjects will be consecutively recruited from women who are scheduled to undergo core needle or surgical biopsy (BIRADS 4 or 5) to have pathological confirmation of malignancy status. Eligible patients will be identified by research staff review in coordination with the UNC Breast Clinic. Once a patient has been referred, the patient will be approached by a coordinator from Radiology to assess interest in participation.

All eligible women who agree to participate in the study will be asked to come to their scheduled biopsy appointment thirty minutes early to complete the informed consent process.

Review of the consent will take place in the privacy of an exam room, or when possible, a sample consent form will be sent to the patient via email prior to the patient's visit to allow for ample review. Once the patient has consented, women of child bearing potential (WCBP) will be given a urine pregnancy test in order to ensure that they are not pregnant. If a urine pregnancy test shows a result positive for pregnancy, the patient will be excluded from the study per the exclusion criteria because the investigators cannot, in good conscience, expose a fetus to the contrast agent used. Women who consent for the study and are eligible will be escorted by the research coordinator to a dressing room, where the subject will change into a gown.

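### The powers in section 10.1 (98%, >96%, 72%) are for a test against b-mode specificity fixed at 70%, not for the primary comparison with b-mode estimated in the same lesions, and the between-modality correlation this needs is not stated

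*Combined protocol and SAP*

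**What the plan says.** Section 10.1 takes as its null hypothesis that "the specificity of acoustic angiography system is the same as the standard of care (b-mode ultrasound), which is assumed to be 70" per cent, with 90% expected for the new device. In that section the trial's own b-mode readings have only a checking role: "We will determine the specificity of b-mode ultrasound during the trial to confirm that the 70% represents the specificity". The clustering assumption is given as "assuming the correlation from the same patient to be 0.5 and the readers to read different patients independently". On this basis, for 60 lesions of which about half are benign, "the power to see specificity at least larger than 90% is 98% at the significance level 0.05 using one-side test". For 50 lesions the stated power is above 96%, and "with 25 lesions (about 13 are benign), this power becomes 72" per cent.

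The aim of the study is comparative. Section 2.1 reads "To compare (using a reader study) the sensitivity and specificity of acoustic angiography to the sensitivity and specificity of conventional b-mode ultrasound", and section 10.0 sets the purpose as to "compare, in a radiologist reader study, the sensitivity and specificity of the acoustic angiography system to the b-mode ultrasound". Section 10.2.1 first plans a reader-averaged estimate for acoustic angiography with a bootstrap standard error and a normal interval. It then plans to estimate b-mode in the same study and to give a bootstrap-based normal interval for the difference. No level or sidedness is given for either interval. Section 4.6 has each reader score each lesion in each modality, so the comparison is paired.

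**The concern.** A test against a constant and a paired difference have different variances. The first contains only the sampling error of acoustic angiography. The second adds the sampling error of b-mode and subtracts twice the covariance between the two modalities' readings of the same lesions. Section 10.1 uses neither term, and no between-modality correlation or discordance rate appears anywhere in the document.

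A colleague who reads 98% beside the primary objective will take it as the probability that the primary comparison succeeds under 90% versus 70%. It is the probability for another test. Because section 10.2.1 does not say whether the interval for the difference is one-sided 5% or two-sided 95%, the power of the planned comparison cannot be worked out from the plan even if a correlation is supplied.

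**Working it through.** **Inputs from section 10.1:** b-mode specificity 0.70; acoustic angiography 0.90; 5 readers; correlation 0.5; one-sided 5%; about 30, 25 and 13 benign lesions out of 60, 50 and 25.

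**1. Reproducing the stated powers.** Treat 0.5 as the between-reader correlation within one modality. The effective number of readings is n × 5/(1 + 4 × 0.5) = 50, 41.67 and 21.67. Against a constant 0.70,

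power = Φ[(0.20 × √n_eff − 1.645 × √0.21)/√0.09].

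- 30 benign: (1.414 − 0.754)/0.3 = 2.20, giving 98.6%
- 25 benign: (1.291 − 0.754)/0.3 = 1.79, giving 96.3%
- 13 benign: (0.931 − 0.754)/0.3 = 0.59, giving 72.3%

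All three match. Alternatives that fail to reproduce the set are a two-sided one-sample test (95.7, 90.5, 54.4%) and two independent proportions, one-sided (81, 74, 50%).

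**2. How uncertain b-mode is on the same inputs.** SE = √(0.21 × 0.6/30) = 0.065, where 0.6 = (1 + 4 × 0.5)/5. The 95% interval is about ±12.7 points with 30 benign lesions.

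**3. Paired difference, normal formula.** Let r be the correlation between a single acoustic angiography reading and a single b-mode reading of the same benign lesion, taken as equal for same-reader and different-reader pairs. It is an assumption; its pairwise maximum at 70% and 90% is (0.70 − 0.63)/√0.0189 = 0.51.

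Var = [(0.09 + 0.21) × 0.6 − 2 × √(0.09 × 0.21) × r]/n; power = Φ(0.20/SE − 1.645).

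With 30 benign lesions, r = 0 gives SE = √(0.18/30) = 0.0775 and power 83%; r = 0.3 gives SE = 0.0570 and power 97%. With 13 the corresponding powers are 52% and 75%.

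**4. The planned method.** The formula departs from the planned interval in small samples, so the interval was simulated: latent-normal readings matched to between-reader correlation 0.5 and to r, patient-level bootstrap standard error in closed form, one-sided 5%, 40,000 trials per cell.

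| Benign lesions | r = 0 | r = 0.1 | r = 0.2 | r = 0.3 | Type I error at 70% vs 70% | Stated power | r at which stated power is reached |
|---|---|---|---|---|---|---|---|
| 30 | 83.5% | 89.1% | 94.6% | 98.6% | about 6% | 98% | about 0.28 |
| 25 | 77.5% | 83.8% | 90.7% | 97.0% | about 6% | >96% | about 0.28 |
| 13 | 57.3% | 64.5% | 72.2% | 83.4% | about 7% | 72% | about 0.20 |

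Type I error above 5% accounts for part of the gap between simulation and formula, mostly at 13 lesions, so these are not powers at an exact 5% level.

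**5. Two sensitivities (normal formula, 30 benign lesions).** With a two-sided 95% interval (1.96 in place of 1.645), power is 73% at r = 0 and 94% at r = 0.3. The definition of r also matters: at r = 0.4 and one-sided 5%, power is 99% as defined above, 94% if r is the correlation of reader-averaged scores, and 87% if it applies to same-reader pairs only.

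**The case against.** **The fixed comparator is disclosed, and part of section 10.2.1 matches it.** Section 10.1 says openly that 70% is assumed and will be checked, and section 10.2.1 begins with a stand-alone acoustic angiography estimate and interval, which a one-sample calculation fits. Both points stand, and they narrow the mismatch. They do not remove it: the objective, the purpose and the primary outcome are worded as comparisons with b-mode, and so is the null hypothesis itself.

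**The 0.5 from the same patient might cover both modalities.** If it did, paired power by the formula would be above 99% with 30 or 25 benign lesions and about 97% with 13. The stated 72% at 13 shows that the calculation did not use it that way. The text does not say that it applies across modalities.

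**No design decision changes.** This is largely right. A reader might infer that the trial is underpowered, or that section 10.1 contains an arithmetic error. The documents support neither. The arithmetic is correct for its test, and "A total of 60 women will be enrolled to this study" gives about 84% simulated power at one-sided 5% even at r = 0, if half the lesions are benign. The figures for 50 and 25 lesions should not be read as planned sizes; the plan does not say why they are shown.

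**Conclusion.** The point holds as a mismatch between the power statement and the primary comparison, together with a missing assumption. The stated powers omit b-mode's sampling error and the between-modality correlation. They overstate the power of the paired difference if r is below about 0.28 (30 or 25 benign lesions) or 0.20 (13), and understate it above those values. At r = 0 the shortfall is about 14 points with 30 benign lesions (98 against 84%) and about 15 with 13 (72 against 57%).

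These sizes rest on the plan's 90%, 70%, 5 readers and 0.5, on one-sided 5%, on a latent-normal model, and on an r that is assumed and taken as equal for all reader pairs. The mismatch itself rests on none of the assumed values. It should be fixed, but it is not a reason to change the sample size.

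**What to change.** **Section 10.1.** Say that 98%, >96% and 72% apply to a one-sided 5% test of acoustic angiography specificity against a fixed 70%, with 0.5 as the between-reader correlation within a modality. Then add the power of the primary comparison, for example:

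*For the paired difference in reader-averaged specificity (90% vs 70%, 5 readers, between-reader correlation 0.5, one-sided 5%), power was obtained by simulating the planned bootstrap interval. With r, the correlation between single readings of the same benign lesion in the two modalities, assumed to lie between 0 and 0.3 and equal for all reader pairs, power is about 84 to 99% with 30 benign lesions, 78 to 97% with 25 and 57 to 83% with 13. The interval's simulated one-sided type I error is about 6%, 6% and 7%.*

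The sponsor should rerun the simulation and give a reason for the range of r.

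**Section 10.2.1.** State the level and sidedness of the interval for the difference so that it agrees with section 10.1: one-sided 5% corresponds to the lower limit of a two-sided 90% interval. If a two-sided 95% interval is intended, restate the power to match.

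**Cost.** A short simulation and a protocol amendment, which section 11.6 requires to have IRB approval before implementation. The stated power becomes less favourable at low r. Enrolment stays at 60, with no extra patients or readings.
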